3.3 Exclusion Criteria

Subject will be excluded from participation if any of the following apply (waivers to the exclusion criteria will **NOT** be allowed):

- 1. Known or suspected neuroendocrine/small cell feature.
- 2. Use of any antineoplastic treatment post-chemotherapy, including but not limited to aminoglutethimide, ketoconozole, abiraterone acetate, Rad-223, sipuleucel-T, or enzalutamide. Continuing steroids is permitted.

- 3. Palliative radiation therapy within 2 weeks of Day 1, or within 4 weeks of Day 1 if a radionuclide was utilized.
- 4. Use of an investigational agent within 4 weeks of Day 1 visit.
- 5. Major surgery within 4 weeks prior to Day 1 visit.
- 6. History of seizure or any condition that may predispose to seizures (e.g., prior cortical stroke or significant brain trauma) at any time in the past. History of loss of consciousness or transient ischemic attack within 12 months of screening.
- 7. History of clinically significant cardiovascular disease including:
 - a. Myocardial infarction or uncontrolled angina within 3 months;
 - b. History of congestive heart failure NYHA class 3 or 4 in the past, unless a screening echocardiogram or multi-gated acquisition scan performed within three months results in a left ventricular ejection fraction that is $\geq 45\%$;
 - c. History of clinically significant ventricular arrhythmias (e.g., ventricular tachycardia, ventricular fibrillation, torsades de pointes);
 - d. History of Mobitz II second degree or third degree heart block without a permanent pacemaker in place.
- 8. Clinically significant cardiovascular disease at screening including:
 - a. Hypotension as indicated by systolic blood pressure < 86 millimeters of mercury (mm Hg) at screening;
 - b. Bradycardia as indicated by a heart rate of < 45 beats per minute on the screening electrocardiogram (ECG) and on physical examination;
 - c. Uncontrolled hypertension as indicated by at least 2 consecutive measurements of a resting systolic blood pressure > 170 mmHg or diastolic blood pressure > 105 mmHg at the screening visit.
- 9. Subject has a known or suspected hypersensitivity to enzalutamide or any components of the formulation used.
- 10. Severe concurrent disease, infection, or co-morbidity that, in the judgment of the investigator, would make the patient inappropriate for enrollment.
- 11. Known or suspected brain metastasis or leptomeningeal disease.
- 12. Gastrointestinal disorder affecting absorption (e.g., gastrectomy, active peptic ulcer disease within last 3 months);
- 13. Absolute neutrophil count < 1,500/μL, platelet count < 75,000/μL, or hemoglobin < 5.6 mmol/L (9 g/dL) at screening.
- 14. Total bilirubin or alanine aminotransferase (ALT) or aspartate aminotransferase (AST) \geq 2.5 times ULN at screening.
- 15. Creatinine $> 177 \mu \text{mol/L}$ (> 2 mg/dL) at screening.
- 16. Albumin $\leq 30 \text{ g/L} (3.0 \text{ g/dL})$ at screening.

17. Treatment with abiraterone acetate prior to enzalutamide for mCRPC in the prechemotherapy setting. (*Note*: Patients who have received concomitant enzalutamide and abiraterone acetate therapies are not excluded).

4 TREATMENT(S)

4.1 Identification of Investigational Product(s)

4.1.1 Test Drug(s)

Enzalutamide is an opaque white to off-white oblong liquid filled soft gelatin capsule for oral administration. Each capsule contains 40 mg enzalutamide.

4.1.2 Comparative Drug(s)

Not applicable.

4.2 Packaging and Labeling

Enzalutamide is supplied by APGD, Medical Affairs, Americas. Enzalutamide will be packaged in high-density polyethylene bottles with child-resistant induction seal closure.

Enzalutamide will be prepared, packaged, and labeled under the responsibility of qualified staff at Astellas US Technologies, Inc. (AUST) in accordance with APGD, Medical Affairs, Americas-AUST Standard Operating Procedures (SOPs), Good Manufacturing Practice (GMP) guidelines, ICH GCP guidelines, and applicable local laws/regulations.

4.3 Study Drug Handling

Enzalutamide will be stored in a secure location with limited access at 20°C to 25°C (68°F to 77°F) with excursions permitted to 15°C to 30°C (59°F to 86°F). Subjects will be instructed to store study drug at room temperature and out of the reach of children.

Current ICH GCP Guidelines require the investigator to ensure that study drug deliveries from the Sponsor are received by the investigator/or designee and

- that such deliveries are recorded.
- that enzalutamide is handled and stored according to labeled storage conditions,
- that enzalutamide with appropriate expiry/retest and is only dispensed to study subjects in accordance with the protocol, and
- that enzalutamide is returned to the Sponsor.

Drug inventory and accountability records for enzalutamide will be kept by the Investigator/or designee. Enzalutamide accountability throughout the study must be documented and reconciled. The following guidelines are therefore pertinent:

- The investigator agrees not to supply enzalutamide to any persons except the eligible subjects in this study in accordance with the protocol.
- The investigator or designee will keep the enzalutamide in a pharmacy or other locked and secure storage facility under controlled storage conditions, accessible only to those authorized by the investigator to dispense enzalutamide.

An enzalutamide inventory will be maintained by the investigator or designee. The
inventory will include details of material received and a clear record of when they
were dispensed and to which subject.

- At the conclusion or termination of this study, the investigator or designee agrees to conduct a final drug supply inventory and to record the results of this inventory on the drug accountability record. It must be possible to reconcile delivery records with those of used and/or returned medication. Any discrepancies must be accounted for and documented. Appropriate forms of deliveries and returns must be signed by the site staff delegated this responsibility.
- The site must return enzalutamide to the Sponsor or designee at the end of the study or upon expiration.

The study sites will provide GnRH agonist or antagonist from pharmacy stock.

4.4 Blinding

This section is not applicable as this is an open-label study.

4.5 Assignment and Allocation

This is an open-label study, so subjects who meet all inclusion criteria and no exclusion criteria will be assigned to begin study treatment. Registration must occur following informed consent process and prior to initiation of investigational therapy. Each site will receive a unique Site ID and each subject at each site will be assigned a subject ID in sequential order as he enrolls in the study. Discontinued subjects will not be replaced.

5 TREATMENTS AND EVALUATION

5.1 Dosing and Administration of Study Drug(s) and Other Medication(s)

5.1.1 Dose/Dose Regimen and Administration Period

Subjects will receive treatment with enzalutamide (160 mg daily), administered as four 40 mg capsules, by mouth, once daily, until radiographic or clinical progression, or unacceptable toxicity.

Study drug should be taken as close to the same time each day as possible. Study drug can be taken with or without food.

Subjects must also be receiving ongoing androgen deprivation therapy with a GnRH agonist, antagonist, or have had a previous bilateral orchiectomy. The study sites will provide GnRH agonist or antagonist from pharmacy stock.

5.1.2 Increase or Reduction in Dose of the Study Drug(s)

Subjects who experience a Grade 3 or greater toxicity considered to be related to enzalutamide that cannot be ameliorated by the use of adequate medical intervention should have their treatment interrupted until the toxicity improves to a Grade 2 or lower severity.

Subjects may subsequently be re-started on study drug at a reduced dose following a discussion between the Investigator and the sponsor.

5.1.3 Previous and Concomitant Treatment (Medication and Non-Medication Therapy)

5.1.3.1 Previous Treatment (Medication and Non-Medication Therapy)

Medication taken within four weeks prior to Baseline (Day 1) and any medications prescribed chronically or intermittently during the study or dose adjustments of these medications must be captured on the case report form.

5.1.3.2 Concomitant Treatment (Medication and Non-Medication Therapy)

Concomitant medications will be captured from the Screening Visit through 30 days after last dose.

Prohibited Medications

The following medications are prohibited while patients are on enzalutamide treatment and have not had disease progression:

- Chemotherapy with anti-tumor activity against prostate cancer such as cabazitaxel, mitoxantrone, etc.
- Sipuleucel-T
- Rad-223
- Androgen-receptor antagonists (bicalutamide, flutamide, nilutamide)
- 5α-reductase inhibitors (finasteride, dutasteride)
- Estrogens
- Cyproterone acetate
- Androgens (testosterone, dehydroepiandrosterone [DHEA], etc.)
- Ketoconazole
- Abiraterone acetate
- Any other investigational agent

Restricted Medications

The dosage and regimen of the following medications and any chronic permitted medications should be stabilized during the screening period (> 4 weeks prior to randomization) and held constant throughout the study:

- Denosumab and bisphosphonates
- GnRH agonist/antagonist therapy

There is a potential for enzalutamide to affect exposures to other medicinal products, or for other medicinal products to affect exposure to enzalutamide:

Strong CYP2C8 inhibitors (e.g., gemfibrozil) or CYP2C8 inducers (e.g., rifampicin)
are to be avoided. If subject must be co-administered a strong CYP2C8 inhibitor, the
dose of enzalutamide should be reduced to 80 mg once daily. If a co-administration of

- the strong inhibitor is discontinued, the enzalutamide dose should be returned to the dose used prior to initiation of the strong CYP2C8 inhibitor.
- Strong CYP3A4 inducers (e.g. carbemezapine, phenobarbital, phenytoin, rifampin) or moderate CYP3A4 inducers (e.g. bosentan, efavirenz, etravirine, modafinil, nafcilin, St. John's Wort) should be avoided if possible as they may reduce enzalutamide plasma concentration if co-administered. Selection of a concomitant medication with no or minimal CYP3A4 induction potential is recommended.
- Enzalutamide is a strong inducer of CYP3A4 and a moderate inducer of CYP2C9 and CYP2C19. Medicinal products with a narrow therapeutic range that are substrates of CYP3A4 (e.g. alfentanil, cyclosporine, dihydroergotamine, ergotamine, fentanyl, pimozide, quinidine, sirolimus, tacrolimus), CYP2C9 (e.g. phenytoin, warfarin), CYP2C19 (e.g. S-mephenytoin), or UGT1A1 should be avoided if possible, as enzalutamide may decrease their exposure.
- If enzalutamide co-administration with warfarin cannot be avoided, additional INR monitoring should be conducted.
- Enzalutamide is an inhibitor of human P-glycoprotein (P-gp) and may increase
 exposure to medicines that are P-gp substrates. Medicinal products with a narrow
 therapeutic range that are substrates for P-gp (e.g., digoxin, colchicine, dabigatran
 etexilate) should be used with caution when administered concomitantly with
 enzalutamide.

No other new systemic therapy or new radiotherapy for treatment (exception for spinal cord compression, pain management, etc.) for prostate cancer is permitted while subject is on the study. Subjects with pre-existing non-target lesions (e.g., bone metastases) receiving palliative radiography for pain treatment before participation in the study are allowed to continue receiving radiotherapy during the study.

5.1.4 Treatment Compliance

Study subjects should be counseled on the need to meet 100% compliance with study drug. Investigator or designee should ensure that study subjects meet this goal throughout the study period. Compliance will be verified by the accounting of study drug at each study visit after Baseline. Compliance of the study drug will be monitored by the accounting of unused medication returned by the subject at visits. Compliance will be documented.

If compliance is less than 80% or more than 120%, the investigator or designee is to counsel the subject and ensure steps are taken to improve compliance. Subjects who are less than 80% or more than 120% compliant with the dosage regimen for any two consecutive visit periods during the study should be withdrawn from the study.

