5.3 Efficacy Assessment

5.3.1 CT/MRI and Bone Scan

Imaging including abdominopelvic CT/MRI, chest CT (if screening chest x-ray leads to diagnosis of thoracic metastasis), and Technicium-99m (Tc-99m) bone scintiography will be performed at the Screening Visit and assessed at Week 9, Week 17, Week 25 and at subsequent 12 week intervals. For subjects that discontinue for reasons other than radiographic progression or initiation of a new anti-neoplastic therapy, the imaging will be conducted every 12 weeks until progression, initiation of new anti-neoplastic therapy, loss to follow-up or death. Imaging performed prior to informed consent may be used as baseline so long as it is performed within the Screening period (days -28 to -1).

Scans should be scheduled in such a way that the scan results are available at the regularly scheduled visit.

The imaging method utilized for baseline scans must be utilized throughout the entire study.

Imaging may be performed at any time to confirm suspected progression of disease.

Radiographic evaluation of metastatic disease is determined separately for soft tissue and bone disease. Radiographic disease assessment for soft tissue disease is based on CT or MRI scan and is defined by RECIST 1.1. Radiographic disease assessment for bone lesions is based on bone scan and progression is considered when a minimum of two new lesions compared to baseline are observed.

Progression on bone scan at time points prior to or at Week 9 require a confirmatory scan performed six or more weeks later. This confirmatory scan should demonstrate at least 2 additional new lesions compared to the Week 9 scan (PCWG2).

Assessment will include tumor measurements for target lesions, non-target lesions, and assessment for any new lesions. An overall assessment will be characterized for that time point evaluation. At the end of study for that subject, the overall best response to the study regimen will be characterized.

Images (abdominopelvic [lung when applicable] CT/MRI and bone scan) should be read on site. Each site should ideally designate the same reader who will evaluate the images for any one subject for the duration of the study.

The same imaging method used for an individual patient at baseline should be used throughout the entire study for that patient.

PET scans should not be used to determine disease progression.

5.3.2 **PSA**

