5.3.4 Survival Follow-up

For all subjects, survival status and subsequent anti-cancer therapies will be followed every 12 weeks for a maximum of 3 years from first dose. The study will end when the last subject has been followed for 1 year from date of first dose.

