6 DISCONTINUATION

6.1 Discontinuation of Individual Subject(s)

A discontinuation is a subject who enrolled in the study and for whom study treatment is permanently discontinued prematurely for any reason.

The subject is free to withdraw from the study treatment and/or study for any reason and at any time without giving reason for doing so and without penalty or prejudice. The investigator is also free to terminate a subject's involvement in the study at any time if the subject's clinical condition warrants it.

If a subject is discontinued from the study with an ongoing adverse event or an unresolved laboratory result that is significantly outside of the reference range, the investigator will attempt to provide follow-up until the condition stabilizes or no longer is clinically significant.

The following events will result in the removal of subjects from enzalutamide therapy:

- Subject develops an adverse event, intercurrent illness, or toxicity, where continued
 administration of study drug is deemed not in the subject's best interest by the
 investigator and/or the sponsor. For example,
 - o Seizure;
 - Posterior Reversible Encephalopathy Syndrome;
 - Laboratory abnormality defined by protocol as follows:
 Creatinine > 354 μmol/L (> 4.0 mg/dL);
 - o AST, ALT, or total bilirubin > 5 times ULN;
 - o Absolute neutrophil count $< 750/\mu$ L;
 - o Platelet count < 50,000/mL.
- Decision by the investigator and subject to initiate a new anti-neoplastic therapy;
- Gross noncompliance with protocol: The medical monitor or investigator may request permanent treatment discontinuation in the event of a major protocol deviation such as administration of prohibited concomitant medication, lack of cooperation, or noncompliance.

Unless the subject withdraws consent, all subjects discontinuing study drug for any reason will have a Safety Follow-up visit 30 days after their last dose of study drug or prior to initiation of subsequent anti-neoplastic therapy for prostate cancer, whichever occurs first.

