Subjects that discontinue study drug for a reason other than radiographic progression or initiation of a new anti-neoplastic therapy will have a PSA test performed 30 days from date of last dose and undergo long-term follow-up every 12 weeks from date of last dose. Long term follow-up will assess for survival, subsequent anti-neoplastic therapy for prostate cancer and radiographic progression. Subjects will be followed for a maximum of 3 years from first dose. The study will end when the last subject has been followed for 1 year from date of first dose. Radiographic imaging will end when the patient has developed a radiographic progression, or initiated subsequent anti-neoplastic therapy. Reasonable effort should be made to contact any subject lost to follow-up during the course of the study in order to complete study related assessments and retrieve any outstanding data and study drug. Following unsuccessful telephone contact, an effort to contact the subject by mail using a method that provides proof of receipt should be attempted. Such efforts should be documented in the source documents.

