8.1.6 Protocol Deviations

A protocol deviation is generally an unplanned excursion from the protocol that is not implemented or intended as a systematic change. The investigator is responsible for ensuring the study is conducted in accordance with the procedures and evaluations described in this protocol and must protect the rights, safety, and welfare of subjects. The investigator should not implement any deviation from, or changes of, the protocol, unless it is necessary to eliminate an immediate hazard to trial subjects.

A protocol waiver is a documented prospective approval of a request from an investigator to deviate from the protocol. Protocol waivers are strictly prohibited.

For the purposes of this protocol, deviations requiring notification to Sponsor are defined as any subject who:

- Entered into the study even though they did not satisfy entry criteria.
- Developed withdrawal criteria during the study and not withdrawn.
- Received wrong treatment or incorrect dose.
- Received excluded concomitant treatment.

When a deviation from the protocol is identified for an individual subject, the investigator or designee must ensure the Sponsor is notified. The Sponsor will follow-up with the investigator, as applicable, to assess the deviation and the possible impact to the safety and / or efficacy of the subject to determine subject continuation in the study.

If a deviation impacts the safety of a subject, the investigator must contact the Sponsor immediately.

The investigator will also assure that deviations meeting IRB/IEC and applicable regulatory authorities' criteria are documented and communicated appropriately. All documentation and communications to the IRB/IEC and applicable regulatory authorities will be provided to the Sponsor and maintained within the Trial Master File (TMF).

NOTE: Other deviations outside of the categories defined above that are required to be reported by the IRB/IEC in accordance with local requirements will be reported, as applicable.

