Severe hepatic liver function abnormalities as defined above, in the absence of another etiology may be considered an important medical event and may be reported as a Serious Adverse Event (SAE). The Sponsor should be contacted and informed of all subjects for

whom severe hepatic liver function abnormalities possibly attributable to study drug are observed.

To further assess abnormal hepatic laboratory findings, the investigator is expected to:

- Obtain a more detailed history of symptoms and prior or concurrent diseases. Symptoms and new onset-diseases should be recorded as 'adverse events' on the AE page of (e)CRF. Illnesses and conditions such as hypotensive events, and decompensated cardiac disease that may lead to secondary liver abnormalities should be noted. Non-alcoholic steatohepatitis (NASH) is seen in obese hyperlipoproteinemic, and/or diabetic patients and may be associated with fluctuating aminotransferase levels. The investigator should ensure that the medical history form captures any illness that pre-dates study enrollment that may be relevant in assessing hepatic function.
- Obtain a history of concomitant drug use (including non-prescription medication, complementary and alternative medications), alcohol use, recreational drug use, and special diets. Medications, including dose, should be entered on the concomitant medication page of the (e)CRF. Information on alcohol, other substance use, and diet should be entered on the LA-CRF or an appropriate document.
- Obtain a history of exposure to environmental chemical agents.
- Based on the subject's history, other testing may be appropriate including:
 - o acute viral hepatitis (A,B, C, D, E or other infectious agents).
 - o ultrasound or other imaging to assess biliary tract disease
 - o other laboratory tests including INR, direct bilirubin
- Consider gastroenterology or hepatology consultations.
- Submit results for any additional testing and possible etiology on the LA-CRF or an appropriate document.

Study Discontinuation

In the absence of an explanation for increased LFT's, such as viral hepatitis, pre-existing or acute liver disease, presence of liver metastases, or exposure to other agents associated with liver injury, the subject may be discontinued from the study. The investigator may determine that it is not in the subject's best interest to continue study enrollment. Discontinuation of treatment should be considered if:

- ALT or AST $> 8 \times ULN$

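### Protocol 5.1.4 tells sites to withdraw non-compliant subjects from the study, while 5.3.1, 5.3.4 and 6.1 stop the drug and keep follow-up: a minor contradiction with a small, conditional effect on rPFS and 1-year survival

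*Protocol*

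**What the plan says.** Protocol 5.1.4 (Treatment Compliance) sets the only numerical compliance trigger. Subjects below 80% or above 120% "for any two consecutive visit periods during the study should be withdrawn from the study".

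Other sections treat stopping the drug and leaving the study as different things:

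- **Protocol 6.1** names them separately: "The subject is free to withdraw from the study treatment and/or study for any reason". It lists gross noncompliance among the events that remove a subject from enzalutamide, and there "The medical monitor or investigator may request permanent treatment discontinuation in the event of a major protocol deviation".
- **Protocol 6.1**, for subjects who stop the drug for a reason other than radiographic progression or new therapy: "Long term follow-up will assess for survival, subsequent anti-neoplastic therapy for prostate cancer and radiographic progression", every 12 weeks.
- **Protocol 5.3.1**, for the same subjects: "the imaging will be conducted every 12 weeks until progression, initiation of new anti-neoplastic therapy, loss to follow-up or death".
- **Protocol 5.3.4**: "For all subjects, survival status and subsequent anti-cancer therapies will be followed every 12 weeks".
- **Protocol 8.1.6** makes it a reportable deviation (coded PD2 in 7.7) if a subject "Developed withdrawal criteria during the study and not withdrawn". It does not say withdrawn from what.
- **SAP 7.2.1** tabulates treatment discontinuation and study discontinuation separately.

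SAP 6.1.1 censors rPFS at the last radiological assessment when there is neither progression nor death. It also censors at the last assessment before any new anti-cancer therapy. SAP 6.1.2 censors overall survival at the last known alive date.

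**The concern.** 5.1.4 and 6.1 cover the same situation but differ in scope (study against treatment) and in force (should against may). Because 5.1.4 carries the numerical trigger, a site is likely to look there first. A site that follows its words ends scans and survival contacts for a subject whom 5.3.1, 5.3.4 and 6.1 would keep. PD2 does not settle the matter: a site that rightly keeps the subject in follow-up could be logged as having failed to withdraw him.

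At stake are later rPFS events and deaths in a 40-subject study whose discontinued subjects are not replaced (Protocol 4.5). Follow-up that was never done cannot be restored at analysis. If non-compliant subjects have the same prognosis as the rest, the loss is precision only. If they do worse, the censoring is informative, and the Kaplan-Meier median rPFS and 1-year survival rate come out somewhat too high.

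**Working it through.** **The plan's own figure.** Protocol 7.1 and SAP 4 give 40 subjects, median rPFS 4 months (exponential), 12 months' uniform accrual, 12 months' minimum follow-up and 10% loss to follow-up. With hazard ln 2/4 = 0.1733 per month and follow-up uniform on 12-24 months:

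- P(event) = 1 − [exp(−12 × 0.1733) − exp(−24 × 0.1733)]/(12 × 0.1733) = 0.9474.
- 40 × 0.9474 = 37.9 events without loss; × 0.90 = 34.1, matching the stated 34.
- Simulated lower 90% bound (log-log Brookmeyer-Crowley): 2.54 months with 36 evaluable subjects and 2.60-2.69 with 40, against the stated 2.5.

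The losses below are computed without loss to follow-up, so they compare with 37.9, not 34.

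**Assumptions, since the documents give no values.**

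- Share affected f = 5%, 10% or 20% (2, 4 or 8 of 40).
- Hazard ratio h = 1, 2 or 3 against the other subjects.
- Withdrawal equally likely at Days 57, 85, 113, 141 and 169. Day 57 is the first visit that closes two visit periods.
- Overall median m = 4 months for rPFS, and 13.6 months for survival (the AFFIRM placebo median in Protocol 1.2, as illustration).
- One month = 30.4375 days.

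**Formulas.** Choose l so that (1−f)exp(−lm) + f·exp(−hlm) = 0.5. Let G(t) be the share of affected subjects not yet withdrawn at t. In large samples the hazard that Kaplan-Meier recovers is

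l[(1−f)e^(−lt) + h·f·G(t)e^(−hlt)] / [(1−f)e^(−lt) + f·G(t)e^(−hlt)],

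integrated numerically to give the apparent median and Day 365 survival. Events lost = 40f × mean over withdrawal times d and follow-up u of [exp(−hld) − exp(−hlu)].

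**Example, f = 20%, h = 1.** The days are 1.873, 2.793, 3.713, 4.632 and 5.552 months. The mean of exp(−0.1733d) is 0.539, and the mean of exp(−0.1733u) is 1 − 0.9474 = 0.0526. Events lost = 8 × (0.539 − 0.0526) = 3.89.

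**Results if follow-up ends at withdrawal:**

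| f | h | rPFS events lost | Median rPFS shift (months) | 1-year survival shift (points) |
|---|---|---|---|---|
| 5% | 1 / 2 / 3 | 0.97 / 0.63 / 0.39 | 0 / 0.021 / 0.026 | 0 / 0.8 / 1.1 |
| 10% | 1 / 2 / 3 | 1.95 / 1.30 / 0.85 | 0 / 0.043 / 0.056 | 0 / 1.5 / 2.2 |
| 20% | 1 / 2 / 3 | 3.89 / 2.78 / 1.98 | 0 / 0.085 / 0.122 | 0 / 3.0 / 4.4 |

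**Allowing for new therapy.** The rPFS columns assume that a retained subject would be scanned to progression or to the end of follow-up. In fact imaging and rPFS stop at new anti-cancer therapy. Let new therapy start at rate k after the drug is stopped (exponential; mean 1/k assumed to be 1 or 2 months). Recoverable events = 40f × mean of exp(−hld) × [hl/(hl+k)] × [1 − exp(−(hl+k)(u−d))]. For f = 20%, h = 1, k = 0.5: 8 × 0.539 × 0.1733/0.6733 = 1.11, the last factor being close to 1.

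| f | h | Recoverable events, mean 2 months | Recoverable events, mean 1 month | Avoidable median shift, mean 2 / mean 1 (months) |
|---|---|---|---|---|
| 5% | 1 / 2 / 3 | 0.28 / 0.25 / 0.19 | 0.16 / 0.16 / 0.13 | up to 0.019 / 0.014 |
| 10% | 1 / 2 / 3 | 0.55 / 0.52 / 0.41 | 0.32 / 0.32 / 0.27 | up to 0.040 / 0.030 |
| 20% | 1 / 2 / 3 | 1.11 / 1.06 / 0.90 | 0.64 / 0.65 / 0.58 | up to 0.088 / 0.067 |

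The survival figures do not change, because survival follow-up continues after new therapy.

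**Sensitivity to timing, before any allowance for new therapy.** Moving rPFS censoring back to the last scheduled scan (Day 57, 113 or 169), as the SAP requires, gives at most 4.2 events and 0.17 months. The extreme case, 20% all withdrawn at Day 57, gives at most 5.4 events, 0.43 months and 5.9 points.

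**Cross-check by paired simulation.** Withdrawing 1, 2 or 4 of 40 subjects at 2-6 months, with hazard ratio 1-2, lost 0.2-1.7 events. It raised the median by at most about 0.05 months, the lower 90% bound by about 0.01 or less, and 1-year survival by at most 1.5 points.

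**The case against.** The strongest reply is that the protocol already answers the question. Section 5.3.1 lists what ends imaging, and noncompliance is not on the list. Section 5.3.4 covers all subjects, and 6.1 files noncompliance under treatment discontinuation. Section 5.1.4 sits under dosing and never mentions follow-up. Appendix 12.2 shows *study* used loosely for treatment: it says "the subject may be discontinued from the study" and then lists criteria for stopping treatment. On this view the harm needs a site to put one loose phrase above several specific ones. That stands as the better reading of intent, and it is why the point is minor. It does not remove the contradiction, because nothing states that 5.3.1, 5.3.4 or 6.1 overrides 5.1.4.

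Two objections to the size also stand. New therapy ends rPFS follow-up in any case, so the larger rPFS figures are upper bounds on what a correction could recover. And the planned 34 events already deduct 10% loss to follow-up, which might absorb some of this attrition.

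A reader might infer that the plan requires follow-up to end for these subjects, or that its rPFS and survival estimates will be biased upward. The documents support neither: other sections direct continued follow-up, and nothing links noncompliance to prognosis. Nor do they support a claim that the sample size is wrong, since its event count reproduces.

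**Conclusion.** The contradiction is real, but it is a minor inconsistency of wording; the follow-up design itself is sound. Any effect needs a site to apply 5.1.4 literally, and any bias also needs non-compliant subjects to do worse.

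Under the base assumptions (5-20% affected, hazard ratio 1-3, withdrawals over Days 57-169), literal use costs up to 0.4-3.9 of about 37.9 rPFS events. It adds up to 0.12 months to the median and up to 4.4 points to 1-year survival. With new therapy a mean of 1-2 months after the drug is stopped, what the correction recovers for rPFS is about 0.1-1.1 events and at most 0.09 months.

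For scale, the planned gap between the assumed median and its expected lower 90% bound is 4 − 2.5 = 1.5 months. With a 13.6-month median, 1-year survival is about 54%, with standard error √(0.54 × 0.46/40), about 8 points. The efficacy endpoints are estimated with 90% confidence intervals, and no success threshold turns on these shifts.

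**What to change.** In Protocol 5.1.4, replace the instruction to withdraw from the study with: *discontinued from study drug, with imaging and survival follow-up continuing per Sections 5.3.1, 5.3.4 and 6.1 unless consent is withdrawn*. Optionally, add to 8.1.6 that for this criterion PD2 means study drug was not stopped.

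The 80% and 120% limits can stay. The cost is one phrase and, if wanted, one further line. No visits are added, because the 12-weekly imaging and survival contacts are already scheduled.
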